13.4.3 Supportive Analyses of the Primary Endpoint(s)/Outcome(s)

Sensitivity analyses will be performed in secondary analyses where associations between change in CD28 expression at week 52 and desensitization are adjusted for age, sex, and allergy type (shrimp, cashew).

13.4.4 Analyses of Secondary and Other Endpoint(s)/Outcome(s)

Similar methods will be used to address secondary objectives. For example, we will regress CD28 expression on a categorical variable for time (baseline, week 52, or week 58), a categorical variable for clinical phenotype (did not achieve desensitization, achieved desensitization but not SU, achieved SU), and their interaction to assess whether trajectories of CD28 over time are differential by response to therapy. Additionally, we will assess whether changes over time in other markers (IFN- γ , IL-4, IL-10, TGF- β , GPR15) vary by response to therapy. We will also examine whether diversity in T cell receptor status at baseline or whether changes in diversity vary by responder status.

All statistical tests will be two-sided and conducted at the 0.05 level of significance. We acknowledge, however, that we are proposing numerous secondary hypotheses and that such an approach can result in false discoveries. We will therefore be fully transparent when reporting any such findings as secondary and hypothesis generating in contrast to how the primary analysis will be reported.

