13.7 Sample Size Considerations

We have excellent power to address our primary objective using the ANCOVA methods. For example, assuming that 81% of subjects achieve desensitization at week 52, we will have approximately 58 responders and 14 non-responders. Given this sample size and group distribution, assuming 2 repeated measurements having a compound symmetry covariance structure, that the correlation between observations on the same subject is 0.5, and assuming a standard deviation for change in CD28 expression on the arc-sin scale at week 52 of 0.90, we have 87% power to detect a difference in change in CD28 expression between responders versus non-

responders of 0.75 on the arcsin scale. If we assume 85% are desensitized, corresponding to 61 responders with assumptions similar to those made above, we have 82% power to detect the same difference. If we consider a 15% missing data on CD28 expression on week 52, we would have 80% power to detect the same change in CD28 expression, assuming 81% are desensitized. If the standard deviation is assumed to be higher – for example due to missing data -- and is as high as 1.1 on the arcsin scale for example, we have 77% power to detect a difference in change between responders and non-responders of 0.85 on the arcsin scale, assuming 81% are desensitized. If we consider a 20% missing data, we would have 78% power to detect the change of 0.85 on the arcsin scale. The treatment effect is assumed to be the same between two foods, however, to ensure that we have enough shrimp allergic participants to detect the SU, we will try to enroll at least 14 participants with shrimp allergies.

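### The CD28 trajectory analysis in 13.4.4 names no within-participant error structure; fitted as written by ordinary least squares, its interaction test is far too conservative and loses substantial power

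*Combined protocol and SAP*

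**What the plan says.** Section 13.4.4 opens with "Similar methods will be used to address secondary objectives", which points back to the primary ANCOVA in 13.4.2. Its worked example has CD28 level as the outcome: "we will regress CD28 expression on a categorical variable for time (baseline, week 52, or week 58), a categorical variable for clinical phenotype". The phenotype levels and the last term are given as "a categorical variable for clinical phenotype (did not achieve desensitization, achieved desensitization but not SU, achieved SU), and their interaction". The purpose given is to see whether CD28 trajectories differ by response to therapy. On testing, the section says "All statistical tests will be two-sided and conducted at the 0.05 level of significance", and it undertakes to report secondary findings as hypothesis generating.

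Nothing in 13.4.4 says how the three samples from one person are linked. The overview in 13.1 lists ANCOVA, Cox regression, LASSO and hierarchical clustering, and none of these supplies a within-person error term for this model. Within-person correlation appears once, in the power calculation for the primary endpoint in 13.7: "assuming 2 repeated measurements having a compound symmetry covariance structure, that the correlation between observations on the same subject is 0.5".

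**The concern.** The primary analysis handles pairing by making change the outcome and baseline a covariate. The trajectory model drops that device: the outcome is the CD28 level, and baseline becomes one level of the time factor. With 72 participants and three visits this gives 216 rows, and nothing in the stated terms ties rows from the same person together.

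The time-by-phenotype interaction is a within-person contrast. If stable differences between people stay in the error term, that contrast is judged against too much variance, and real differences in trajectory can be missed. This is the worked example for the first-listed secondary endpoint, in a study whose stated purpose is mechanistic. Leaving the error structure open also allows it to be chosen after the data are seen.

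**Working it through.** **Inputs from the plan.** N = 72, with 58 desensitized and 14 not (13.7). Three times and three phenotypes (13.4.4), so the interaction has 4 df. Two-sided alpha 0.05. SD: "assuming a standard deviation for change in CD28 expression on the arc-sin scale at week 52 of 0.90". Difference between groups: "responders of 0.75 on the arcsin scale". Correlation rho = 0.5, given in 13.7 for two measurements and extended here to three. At rho = 0.5 the SD of change equals the SD of one measurement, because sqrt(2(1 − 0.5)) = 1, so 0.90 serves for both.

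**Assumptions not in the plan.** Compound symmetry over three visits, complete data, a 29/29 split of the 58 desensitized participants into those with and without sustained unresponsiveness (SU), and the effect patterns at week 58.

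**1. The plan's own figure.** No size or power is stated for the interaction test. For the primary test, 13.7 states 87%. A two-sided ANCOVA t-test with variance factor 1 − rho² = 0.75 has SE = 0.90 × sqrt(0.75) × sqrt(1/58 + 1/14) = 0.232. The ratio is 0.75/0.232 = 3.23, and power is 89.0%, within two points. For 61/11 the same formula gives 82.5%, against 82% stated. A one-sided t-test on change gives 87.0% and 80.9%, so the exact formula is not identified. The inputs are nevertheless on the right scale.

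**2. What ordinary least squares does to the error term.** Under compound symmetry, with measurement variance σ²:
- the between-person mean square (69 df) has expectation σ²(1 + 2rho);
- the within-person mean square (138 df) has expectation σ²(1 − rho);
- the pooled residual (207 df) has expectation [69(1 + 2rho) + 138(1 − rho)]σ²/207 = σ².

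Under the null the interaction mean square has expectation σ²(1 − rho), but it is divided by about σ².

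**3. Size.** Approximately P[F(4,207) > F₀.₉₅/(1 − rho)], with F₀.₉₅(4,207) = 2.415.

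| rho | effective cut-off | size |
|---|---|---|
| 0 | 2.415 | 5.0% |
| 0.1 | 2.68 | 3.3% |
| 0.3 | 3.45 | 0.9% |
| 0.5 | 4.83 | 0.10% |
| 0.7 | 8.05 | below 0.001% |

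Simulation at rho = 0.5 gives 0.10% to 0.13% over three splits of the 58 (29/29, 15/43, 43/15). A test with within-person error (4 and 138 df) gives about 5%.

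**4. Power at a difference of 0.75, rho = 0.5.** For a shift d at weeks 52 and 58 in n₁ of the 72 people, the noncentrality is [n₁(72 − n₁)/72] × (2/3)d² / [σ²(1 − rho)]. Here (2/3)d² = 0.375 and σ²(1 − rho) = 0.81 × 0.5 = 0.405.
- Only the SU group shifts: (29 × 43/72) × 0.375/0.405 = 16.0.
- Both desensitized groups shift: (58 × 14/72) × 0.375/0.405 = 10.4.

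| Pattern | within-person error | least squares |
|---|---|---|
| Only SU shifts | about 90% | about 50% |
| Both desensitized groups shift | about 73% | about 24% |
| Graded shift | 65% | 18% |
| Both shift at week 52, SU failures revert by week 58 | 97% | 70% |

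As a general guide at rho = 0.5, a test with 80% power under the correct error has 32% under least squares, and one with 90% has 49%.

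**The case against.** The plan never says that the samples are independent. A reader might infer that from the list of terms, but a mixed model or GEE is also a regression, the text is introduced as an example, and 13.7 shows that the authors expect within-person correlation. This stands. The defect is that the error structure is not stated, and the figures apply only if the model is fitted as written by least squares.

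Three other strong readings are not supported:
- **That the test loses most of its power.** This is true for some patterns (73% to 24%, 65% to 18%) but not for others (90% to 50%, 97% to 70%).
- **That group differences averaged over time would be overstated or falsely declared.** The plan proposes the interaction test, not a phenotype main-effect test. With complete data, least squares does not inflate the estimated difference. For the planned test the error is conservative.
- **That the same model is prescribed for the other markers.** Section 13.4.4 says only that their changes over time will be compared by response. An analysis of change scores would already respect the pairing, so carry-over is implied at most.

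Finally, the analysis is secondary and labelled hypothesis generating. That limits the severity. The label guards against false discoveries, however, and gives no protection against missing real differences.

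**Conclusion.** The point holds as an omission with a quantifiable consequence. Section 13.4.4 lists the terms of the trajectory model without any provision for three samples per participant. Under least squares the nominal 5% interaction test has a size of about 0.1% at the plan's own correlation. It is conservative at any positive correlation under compound symmetry. The loss of power is substantial, but how large depends on the effect pattern and on an SU split that the plan does not give. The correlation of 0.5 is itself borrowed from a two-measurement calculation for another analysis.

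Severity is moderate. The primary ANCOVA in 13.4.2 handles pairing through change and baseline, and it is untouched.

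**What to change.** State in 13.4.4 that the trajectory analysis uses a linear mixed model for repeated measures with the fixed effects already listed, an unstructured within-participant covariance (or at least a random participant intercept), and a test of the time-by-phenotype interaction. Apply it to CD28 and to each continuous secondary marker in 3.3 and 13.2.2 that is analysed over time. That includes CCR4 and CRTh2, which 13.4.4 does not list.

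The CD28 endpoint in 3.3 runs to week 64, so include those samples where available. Section 3.1 offers week 64 only to participants who pass at week 58, so the other two phenotypes will have little or no week-64 data. The text should say that the three-group interaction is tested through week 58 and that week 64 extends the SU trajectory.

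The cost is a few sentences in the analysis plan, settled before the secondary analysis is run. No new data, visits or participants are needed.

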13.4.5 Analyses of Exploratory Endpoint(s)/Outcome(s)

There are numerous questions of interest that involve the utility of data generated on a variety of platforms for predicting clinical response, or for describing other relevant clinical phenotypes that could provide insight into OIT. An important goal is to identify those with potential ability to discriminate across phenotypes relevant for characterizing and treating patients with significant FA. Thus, for each platform of interest, we will evaluate the roles of mechanistic features in predicting SU and control the false discovery rate (FDR) to be no more than 5%. In addition to statistical testing, analyses (e.g., those that employ LASSO) will jointly evaluate features and identify those with relatively more importance with respect to the clinical phenotype of interest. Additionally, other analyses (such as hierarchical clustering) will provide graphical depictions of clustering of features and of subjects, providing insight into features within and across platforms and potentially meaningful clinical phenotypes. Similar to our approach for secondary analyses, we will be fully transparent in reporting any findings as exploratory and hypothesis generating in contrast to how the primary analysis will be reported.

13.4.6 Descriptive Analyses

Means, medians, standard deviations, and interquartile ranges will be presented for continuous variables. Frequency tables will be provided for categorical and discrete terms, such as family history and ethnicity. Graphical tools such as boxplots and histograms will be used to assess distributional properties of continuous variables. Transformations for primary and secondary endpoints may be necessary to better adhere to modeling assumptions. For example, expression of CD28 may be log- or arcsin-transformed prior to analysis.

Covariates and Confounders

For all statistical analyses that yield estimates of associations, we will provide unadjusted associations of relevant quantities as well as associations that adjust for pre-specified confounders. Comparisons between unadjusted and adjusted associations will provide insight into how estimates vary through associations.

Effect Modification

To evaluate effect modification of an exposure-outcome association by risk for FA, we will rely on interaction terms in the model to assess the statistical significance of any observed difference in association among levels of the potential effect modifier. These analyses are not specified in our primary analysis but may be included in exploratory analyses.

13.5 Interim Analyses

Interim analysis to investigate the change of CD28 from baseline is planned when 30 participants (either cashew or shrimp) are enrolled and complete the CD28 measurement at week 52.

13.5.1 Interim Analysis of Efficacy Data

The interim analysis for an early evaluation of the change in CD28 from the baseline will be conducted after 30 participants are enrolled and complete the CD28 measurement at week 52. We designed the interim analysis for early stopping when we rejected the null hypothesis with a significant difference of changes on CD28 expression compared to baseline. The O'Brien-Fleming decision boundary is used to control the overall type I error probability at the conventional 0.05 level. The Lan-DeMets error-spending approach that approximates O'Brien-Fleming is used to determine the alpha with the information fraction of 41.7%. The interim analysis stage, the null hypothesis will be rejected if the test is significant at the alpha level of 0.001 with an associated absolute Z statistic of 3.28. Thus the trial will be stopped if the test statistic is less than or equal to -3.28 or greater than or equal to 3.28 with p value ≤ 0.001 ; otherwise the null hypothesis will be accepted and the trial will be continued.

Considering the possibly slow pace of participant enrollment, we will conduct our interim analysis based on data accumulated by January 31, 2021, if the pre-planned information fraction of 41.7% is not reached by that time. We will use the Lan-DeMets O'Brien-Fleming error-spending approach to determine the corresponding alpha and boundary based on the true information fraction.

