1.2. Rationale for Selection of Investigational Product or Intervention

We have designed the primary endpoint based on preliminary mechanistic understandings of T cell modifications over time during immunotherapy. When first activated, T-cells initially start making Th2 products like IL4 and IL13, but over the course of therapy they start making more interferon gamma and start expressing less CD28 so that they appear more anergic (Ryan et al. PNAS 2016; Syed, et al. JACI 2014; Pellerin, et al. JACI 2018). The hypothesis would be to expect a change of 20% in the T cell population to shift within 52 weeks toward this activated allergen-specific subset that makes interferon gamma and is more anergic. Exploratory endpoints will include the changes in the transcriptomes and phenotypes of tetramer+ T cells from baseline to 52 weeks, 58 weeks and to 64 weeks.

Our and others' community-based participatory research⁷⁻⁹ show that many patients and families would prefer to be desensitized to a low dose of FA protein (300mg) to avoid worry about accidentally eating a contaminated food, while others would prefer to safely ingest a larger dose of FA protein (1,000 mg or more) to be able to try certain foods containing the FA; therefore, we have proposed using these two quantities in our clinical study as the treatment dose (1000 mg) and the desensitization threshold (2,043 mg). There are several lines of evidence (Jones, et al. AAAAI, 2018, Phase 3 results of PALISADES study and Andorf, et al. AACI 2017

<https://www.ncbi.nlm.nih.gov/pmc/articles/PMC5738818/>) demonstrating that 300 mg of maintenance of each food allergen protein will allow some protection in the majority of participants to at least 1000 mg of each food allergen protein during a standardized food challenge. However, recent data has shown that maintenance at higher levels (i.e. 1000 mg) would afford protection to higher levels of accidental ingestion (for shrimp, since the average shrimp is approximately 8g, we prefer to propose 1000 mg maintenance in this study) and perhaps could improve SU outcomes.

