13.2 Endpoints and anticipated results

13.2.1 Primary Endpoint(s)/Outcome(s)

Change in expression of CD28 in the CD4+ allergen specific (CD154+) T-cells at 52 weeks relative to baseline values between those who do and do not pass the DBPCFC at week 52 at a cumulative tolerated dose of 2043 mg.

i.e. Comparing those who pass the desensitization challenge vs all others there will be at least a 20% increase in the allergen specific (CD154+) T-cell activation towards a Th1/ anergic state at week 52 DBPCFC.

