13.4.2 Primary Analysis of Primary Endpoint(s)/Outcome(s)

We will rely on analysis of covariance (ANCOVA) methods to model the change of CD28 expression measured at week 52 from baseline as a continuous variable as a function of: the baseline CD28 measurement and an indicator for whether the subject passed the DBPCFC at week 52, where the parameter for the latter is of main interest and represents whether changes in expression of CD28 differ for those who achieve desensitization versus those who do not. We will test whether the parameter of interest differs significantly from zero using a two-sided F-test at the 0.05 level of significance.

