13.6 Statistical Hypotheses

Our hypothesis is that CD28 expression in the allergen specific (CD154+ or tetramer+) T-cell activation towards a Th1/ anergic state at week 52 DBPCFC relative to baseline will be significantly decreased among those who achieve desensitization versus those who do not.

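### The interim efficacy stop is described only as CD28 change from baseline and does not name the week 52 pass/fail contrast that is the primary hypothesis

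*Combined protocol and SAP*

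**What the plan says.** The interim analysis is described three times, each time with baseline as the only stated reference.

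- Section 13.5: "Interim analysis to investigate the change of CD28 from baseline is planned when 30 participants (either cashew or shrimp) are enrolled" and have their week 52 CD28 measurement.
- Section 13.5.1, opening: "The interim analysis for an early evaluation of the change in CD28 from the baseline will be conducted" at that same point.
- Section 13.5.1, stopping criterion: "early stopping when we rejected the null hypothesis with a significant difference of changes on CD28 expression compared to baseline".

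Section 13.5.1 then sets a Lan-DeMets O'Brien-Fleming boundary at an information fraction of 41.7% (alpha 0.001, absolute Z 3.28) and claims overall type I error control at 0.05. It says that, if the boundary is not crossed, the null is accepted and the trial goes on. The look was to use data to January 31, 2021 if the planned fraction had not been reached by then.

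The primary question is a comparison of groups. In 13.4.2 the ANCOVA parameter for passing the week 52 challenge is the one of interest; it "represents whether changes in expression of CD28 differ for those who achieve desensitization versus those who do not". The final test reads: "We will test whether the parameter of interest differs significantly from zero using a two-sided F-test at the 0.05 level of significance". Section 13.6 hypothesises that CD28 expression relative to baseline "will be significantly decreased among those who achieve desensitization versus those who do not".

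**The concern.** The only rule that can end the trial early for efficacy does not say which statistic it uses. A statistician working from 13.5 and 13.5.1 could in good faith run a paired test of week 52 against baseline in all 30 participants, or could test the pass/fail coefficient of 13.4.2.

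The two can disagree. Section 1.2 expects T cells to change with treatment: "over the course of therapy they start making more interferon gamma and start expressing less CD28 so that they appear more anergic". It draws no line there between participants who later pass and those who fail, so some fall common to both is plausible. A pre/post test would pick up that fall even with no difference between the groups. The trial could then stop with the primary question unanswered and fewer than half of the planned participants contributing. What is at stake is a stop on the wrong question, not a false positive on the primary null.

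**Working it through.** **1. The plan's own boundary.** Inputs from 13.5.1 and 13.7: 30 of 72 participants, overall two-sided 0.05 (0.025 per side).

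- t = 30/72 = 0.4167.
- Spend = 2 × [2 − 2Φ(2.2414/√0.4167)] = 2 × [2 − 2Φ(3.472)] = 0.00103, so Z = 3.282.

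The stated 0.001 and 3.28 reproduce. The boundary is not in error.

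**2. Pre/post reading, equal fall in both groups.** Inputs: n = 30; SD of change 0.90, and 1.1 as the plan's higher case (both 13.7); two-sided p ≤ 0.001. The size of the shared fall is assumed, because the documents give none. The paired t-test has 29 df, critical value 3.659 and noncentrality fall × √30/SD. For example, 0.45 × √30/0.90 = 2.74.

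| Assumed shared fall (arcsin scale) | P(stop), SD 0.90 | P(stop), SD 1.1 |
|---|---|---|
| 0.20 | 1.5% | 0.9% |
| 0.45 | 21% | 11% |
| 0.75 | 80% | 54% |

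**3. Contrast reading, same data.** The 81% pass rate in 13.7 gives 0.81 × 30 ≈ 24 passing and 6 failing. A shared fall cancels out of the pass/fail coefficient, so it crosses p ≤ 0.001 in about 0.1% of trials whatever the fall. Simulation with 100,000 datasets per scenario and baseline/week 52 correlation 0.5 gave 0.10% to 0.12%.

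**4. Contrast reading, planned difference of 0.75 present.** Residual SD = 0.90 × √(1 − 0.5²) = 0.779. Noncentrality = 0.75/[0.779 × √(1/24 + 1/6)] = 2.11 on 27 df. P(stop) is about 8%.

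**5. Smallest observed effect that reaches Z = 3.28 (SD 0.90, unadjusted).**

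- Pre/post: 3.28 × 0.90/√30 = 0.54, as a mean change.
- Contrast: 3.28 × 0.90 × √(1/24 + 1/6) = 1.35, as a difference between groups.

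**6. Type I error under the contrast reading.** With 0.00103 spent at t = 0.4167, exact control needs a final Z of 1.963 (two-sided p 0.0497). Section 13.4.2 instead tests at 0.05 (Z 1.960). Overall error = 1 − P(|Z₁| < 3.28, |Z₂| < 1.960), with correlation √t and contrast information t = (1/58 + 1/14)/(1/pass + 1/fail).

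| Interim split (pass/fail) | Information | Overall error |
|---|---|---|
| 24/6 | 0.426 | 0.0503 |
| 26/4 | 0.307 | 0.0505 |
| 27/3 | 0.239 | 0.0506 |

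For any split it cannot exceed 0.05 + 2 × P(Z > 3.28) = 0.0510.

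**The case against.** The best defence is that the documents already point to the contrast. The stopping sentence speaks of a difference of changes, and a pre/post test assesses a change, not a difference between changes. Its reference to baseline can be read as saying what each change is measured from. The section refers to a single null and spends a single overall 0.05, and the only primary null specified at that level is the pass/fail parameter. The fraction 30/72 is tied to a sample size that 13.7 justifies for responders against non-responders. The 20% target in 13.2.1 is stated between groups: "Comparing those who pass the desensitization challenge vs all others there will be at least a 20% increase".

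Most of this stands, and it rules out two stronger readings.

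- A reader might infer that the rule as written simply is a pre/post test. The documents do not support that; the wording is ambiguous and leans towards the contrast. It does not settle the matter, though. The groups are never named, and 1.2 and 13.7 give the same 20% without groups, in 13.7 as a change against baseline.
- A reader might take the 80% as a forecast. It is not. It takes 0.75, the planned difference between groups, as a fall common to both. The expected-results table in Section 9 lists decreased CD28 under desensitization and SU and says nothing about those who fail.

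Timing also limits the benefit. The look was due on data to January 31, 2021 at the latest, and the page footer dates this text Version 4.0, 26 May 2022. If the look has been done, new wording cannot prevent a wrong stop, and the useful step is to record what was tested.

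**Conclusion.** The point holds as a gap in specification, of minor to moderate severity. Sections 13.5 and 13.5.1 do not tie the interim test to the primary contrast, and a rule that can end the trial should not depend on inference. The two admissible readings behave very differently. With a shared fall and no group difference, the pre/post test stops in 1.5% to 80% of trials over the assumed falls at SD 0.90, against about 0.1% for the contrast. That range rests on n = 30, equal falls in both groups and fall sizes that the documents do not supply, so it shows the direction of the problem and is not a prediction.

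A reader might also infer that type I error is materially inflated. It is not under the contrast reading: leaving the final test at 0.05 gives about 0.0503 against the 0.05 claimed. That is a real inconsistency between 13.4.2 and 13.5.1, but a small one.

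**What to change.** - In 13.5.1, state that the interim statistic is the pass/fail coefficient from the 13.4.2 ANCOVA, and that the trial stops only if its two-sided p is at or below the Lan-DeMets value (0.00103 at 41.7%).
- In 13.4.2, set the final level to the remaining boundary: 0.0497 for a look at 41.7%, recomputed if the actual fraction differs.
- In 13.5.1, drop the statement that the null is accepted when the boundary is not crossed, and say only that the trial continues.
- If the look has already taken place, record which statistic was tested, the information fraction and the alpha spent. The final level needs adjusting only if the look tested the contrast.

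The cost is a few sentences and, where applicable, a record of the look. The sample size does not change, and the final level moves from 0.0500 to 0.0497.
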